3.4.2 Patient-Reported Outcomes

Patient-reported outcomes (PROs) of lung cancer-related symptoms (i.e., cough, dyspnea, pain in chest, pain in arm/shoulder) will be assessed using the EORTC QLQ LC13 (Bergman et al. 1994). Summary statistics (mean, SD, median, and range) of linear transformed scores will be reported for all the items and the dyspnea subscale of the EORTC QLQ-LC13 according to the EORTC scoring manual guidelines. The mean change of the linear transformed scores from baseline will also be assessed as well as the proportion of patients with improved, stable, or worsened outcomes.

Completion and compliance rates will be summarized at each time point will be calculated as the number of patients who completed the assessment divided by the number of patients expected to complete the assessment at each time. Reasons for missing assessments, if available, will be summarized using frequencies and percentages.

The analysis of PRO measures will be conducted on the safety population, and will include all assessments until progressive disease as per RECIST 1.1. All assessments performed strictly after progressive disease as per RECIST 1.1 will only be listed.

The percentage for baseline will be calculated based on safety population. Only patients with a baseline assessment and at least one non-missing post-baseline assessment will be included in the analyses.

Time to Confirmed Symptom Deterioration (TTCSD):

Time to confirmed symptom deterioration using the EORTC symptom scores is defined as the time from baseline to the first confirmed clinically meaningful deterioration in the EORTC symptom score. Confirmed clinically meaningful deterioration in lung cancer symptoms is defined as a ≥ 10 -point increase above baseline in a symptom score that must be held for at least two consecutive assessments or an initial ≥ 10 -point increase above baseline followed by death within 3 weeks from the last assessment. A ≥ 10 -point change in the EORTC scale score is perceived by patients as clinically significant (Osoba et al. 1998).

TTCSD will be documented for each of the following EORTC-based symptom scores:

- Cough (Question 31 on the EORTC QLQ-LC13)
- Chest pain (Question 40 on the QLQ-LC13)
- Dyspnea multi-item subscale (Questions 33-35 on the QLQ-LC13)
- Arm and/or shoulder pain (Question 41 on the QLQ-LC13)
- Composite of the 3 symptoms: cough, dyspnea (multi-item subscales QLQ-LC13) and chest pain

If no baseline or post-baseline assessment is performed, patients will be censored at the start date of study treatment plus 1 day. Patients without deterioration at the time of clinical cut-off date will be censored at the last time they were known to have not deteriorated.

TTD of the pre-specified symptoms will be summarized using the Kaplan-Meier method. The median time and two-sided 95% CI for the median will also be provided.

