Schedule of Assessments (cont.)

	Screening Period		Treatment Period	Treatment Discontinuation	Follow-Up Period
	Day -28 to Day -1	Day -14 to -1	Day 1 (\pm 5 days) of each 3-week treatment cycle	\leq 30 days from last dose or at initiation of new anti-cancer therapy (whichever occurs first)	
Pregnancy test ^m		x	Every 3 cycles		
Tumor assessment ⁿ	x ^o		Every 6 weeks for 48 weeks, thereafter every 9 weeks until PD (regardless of atezolizumab discontinuation) or until loss of clinical benefit for patients treated beyond progression ^p		
EGFR/ALK testing ^q	x				
Submission of pre-treatment tumor tissue (biomarker) ^{r, s}		x ^u			
Plasma for RBR (optional) ^t		x ^u		PD	
EORTC QLQ-LC13 & EQ-5D-5L ^v			Day 1 of first 3 cycles, then with tumor assessments		
Concomitant medications ^w	x		x	x	
Adverse events ^x	x		x	x	x
Study drug infusion			x		
Survival and new anti-cancer therapy ^y				x	x

Abbreviations: aPTT: activated partial thromboplastin time; ECG: electrocardiogram; ECOG: Eastern Cooperative Oncology Group; EORTC: European Organisation for Research and Treatment of Cancer; INR: international normalized ratio; PD: progressive disease; PRO-CTCAE: Patient-Reported Outcomes Version of the Common Terminology Criteria for Adverse Events

Note: Unless otherwise indicated, assessments scheduled on the study treatment days should be performed prior to initiation of study treatment infusion.

a. Written informed consent is required for performing any study-specific tests or procedures. Results of standard-of-care tests or examinations performed prior to obtaining informed consent and within 28 days prior to study entry (except where otherwise specified) may be used for screening assessments rather than repeating such tests.

Appendix 1

Schedule of Assessments (cont.)

- b. Medical history includes surgical and cancer histories. Cancer history includes stage, date of diagnosis, prior anti-cancer treatment, EGFR/ALK status and, if available, PD-L1 status. Reproductive status and smoking history should also be captured. Demographic information includes age, sex, and self-reported race/ethnicity.

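### Symptom worsening first seen at the progression visit cannot be confirmed by a second analysed questionnaire, so it is censored and time to deterioration looks longer

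*SAP*

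**What the plan says.** SAP 3.4.2 sets one inclusion rule for all patient-reported outcomes. The analysis "will include all assessments until progressive disease as per RECIST 1.1", while "All assessments performed strictly after progressive disease as per RECIST 1.1 will only be listed". No exception is made for time to confirmed symptom deterioration (TTCSD), which is defined in the same section.

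A TTCSD event is an increase of at least 10 points that "must be held for at least two consecutive assessments", or a single such increase "followed by death within 3 weeks from the last assessment". Patients without an event "will be censored at the last time they were known to have not deteriorated". The estimator is stated as "TTD of the pre-specified symptoms will be summarized using the Kaplan-Meier method", with a median and two-sided 95% CI. There are five results: cough, chest pain, dyspnea, arm or shoulder pain, and a three-symptom composite.

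The Schedule of Assessments (Protocol Appendix 1, repeated in SAP Appendix 2) gives the questionnaires on "Day 1 of first 3 cycles, then with tumor assessments". Scans are 6-weekly to week 48 and 9-weekly afterwards. They end at progression, except in patients treated beyond it, who are scanned until loss of clinical benefit.

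**The concern.** A confirmation rule needs a later observation, and the progression cut-off removes it exactly when symptoms are likely to worsen. A patient whose cough first worsens at the scan that shows progression has one worsened questionnaire in the analysis set and cannot have a second. The patient is censored, although the reason for the censoring is the worsening that the endpoint is meant to detect.

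Kaplan-Meier assumes that censored patients have the same future risk as those who stay at risk. Here the censored patients have just worsened. The result is a longer apparent time to deterioration in a single-arm trial, with no control arm in which the same distortion would appear. Progression is not named as an event, a competing event or a censoring reason for TTCSD. The sensitivity analysis in SAP 3.4.3.4 covers only OS and PFS.

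**Working it through.** The documents give no expected median, event count or precision for TTCSD, so there is no figure to reproduce. The check has a logical part and an illustrative numerical part.

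**Logic, from the visit grid.** Nominal questionnaires fall at weeks 0, 3, 6, 12, 18 and so on.

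- Progression at week 6: the analysed post-baseline questionnaires are weeks 3 and 6. The only confirming pair is 3+6, so the worsening must already be present at week 3.
- Progression at week 12: the pairs are 3+6 and 6+12, so it must be present by week 6.
- In general, the worsening must be present at the questionnaire before the progression visit. One that first appears at the progression visit can become an event only through the death clause.

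**Censoring date.** Read literally, the last time known not to have deteriorated is the visit before the worsening. If an unconfirmed increase is instead taken as not deteriorated, the patient is censored at the progression visit and counts as event-free up to then. The event is lost on both readings, and the second leaves the curve slightly higher.

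**How many patients progress early.** Assume exponential PFS, with medians of 2.3 to 4.0 months. This is the range for second-line anti-PD-1 agents in Protocol Table 3; the trial has no planning value of its own. Share progressed by time t = 1 − 2^(−t/median).

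- 6 weeks = 42/30.44 = 1.38 months: 1 − 2^(−1.38/2.3) = 34%; 1 − 2^(−1.38/4.0) = 21%.
- 12 weeks = 2.76 months: 56% and 38%.

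**Illustrative simulation** (200,000 patients per scenario, documented visit grid). Every rate is an assumption: background worsening with a median of 8 months; an extra 0%, 20% or 40% of patients worsening in the interval that ends at the progression visit; 0%, 30% or 50% treated beyond progression; 0%, 5% or 10% dying within 3 weeks of the progression questionnaire; every worsening lasting. Deterioration-free estimate at 24 weeks, selected scenarios:

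| Median PFS (months) | Extra worsening at PD | Treated beyond PD | Early death | SAP rule | Post-PD forms may confirm | Worsening at PD counted unconfirmed |
|---|---|---|---|---|---|---|
| 4.0 | 0% | 30% | 5% | 67.3% | 65.7% | 62.1% |
| 4.0 | 20% | 30% | 5% | 65.8% | 61.2% | 52.1% |
| 2.3 | 20% | 50% | 5% | 68.6% | 56.5% | 46.9% |
| 2.3 | 40% | 50% | 5% | 65.7% | 47.2% | 34.5% |
| 2.3 | 40% | 0% | 0% | 68.0% | 68.0% | 34.5% |

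Across the scenarios with 30% to 50% treated beyond progression and 5% to 10% early death, the SAP rule exceeds post-progression confirmation by 67.3 − 65.7 = 1.6 to 65.7 − 47.2 = 18.5 percentage points. In those scenarios it censors 17% to 62% of first worsenings seen at or before progression. The shift is upward even with no extra worsening at progression (first row), because the censoring depends on the worsening itself. The last row shows that allowing post-progression confirmation changes nothing if nobody is treated beyond progression.

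**The case against.** Four objections carry weight.

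- **The death clause.** A reader might infer that worsening at progression can never be confirmed, or that a patient who progresses at the first scan and has only the Cycle 2 questionnaire left cannot have an event. The documents do not support either: a single worsening followed by death within 3 weeks of the last assessment counts. What is closed is confirmation by a second questionnaire.
- **The progression-visit questionnaire is normally kept.** A reader might infer that it is routinely lost because it is dated after the scan. Protocol 4.5.9 puts questionnaires before other assessments and before any news of disease status, and only those strictly after progression are excluded, so a same-day form stays in. The residual risk is chiefly at week 6. There the form is tied to Cycle 3 Day 1 while the scan has its own ±5-day window (Protocol 4.5.5), and the SAP has no rule linking the two.
- **Post-progression data are sparse and selected.** A reader might infer that the SAP throws away data that would settle the matter. Those forms are listed, not discarded, and they are scheduled only for patients treated beyond progression. Protocol 4.6.2 requires such patients to have stable or improved disease-related symptoms. For everyone else the limit is the collection schedule. The simulation assigned treatment beyond progression independently of symptoms, so it probably overstates what post-progression confirmation would recover.
- **Low stakes.** Requiring confirmation and stopping at progression are legitimate pre-specified choices. SAP 3.4 calls all efficacy analyses descriptive, and TTCSD appears only in the SAP; the protocol's endpoint is the QLQ-LC13 score.

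All four narrow the point. None supplies a second analysed questionnaire for a worsening first seen at the progression visit, and none provides a check on the resulting estimate.

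**Conclusion.** The concern stands in a limited form. Followed as written, SAP 3.4.2 censors worsening first seen at the progression visit unless early death follows, and so produces TTCSD curves and medians that look longer. The direction follows from the text, provided that at least some of these worsenings last, and it strengthens if worsening clusters at progression, as is plausible.

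The size is not established. The range of 1.6 to 18.5 percentage points at 24 weeks rests on assumed rates of progression, worsening, treatment beyond progression and early death, and on every worsening being permanent. If some are transient, the bias is smaller, and it should not be quoted as an estimate for this trial. The effect is confined to five descriptive patient-reported results; the primary safety endpoints are untouched.

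**What to change.** Amend SAP 3.4.2, for TTCSD only:

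1. **Main change.** Add a pre-specified sensitivity analysis that counts a worsening of at least 10 points at the last questionnaire on or before progression as an event when no later analysed questionnaire exists. SAP 3.4.1.6, criterion (a), already takes this approach for modified-RECIST progression with no subsequent tumor assessment. Because it also counts transient worsening, present it beside the confirmed analysis.
2. Treat the questionnaire linked to the progression scan, within the visit window, as on or before progression. This matters chiefly at Cycle 3 Day 1. State also the censoring date for a patient with a single unconfirmed worsening.
3. As a supportive analysis only, let available post-progression questionnaires confirm a worsening first seen on or before progression, with a note that they come from patients selected for stable or improved symptoms.

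The cost is SAP wording, one extra sensitivity table and the supportive output. No new data are needed. The reported times to deterioration will be less favourable.

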3.4.3 Exploratory Efficacy Endpoints

3.4.3.1 PFS from Start of New Anti-Cancer Therapy

For patients who started a new anti-cancer therapy, PFS from start of new cancer therapy is defined as the time (in months) from start of new anti-cancer treatment to the first occurrence of disease progression on next-line treatment or death from any cause, whichever occurs first.

Patients who are alive and who have not experienced disease progression on next-line treatment at the time of clinical cut-off date will be censored at the last date known to be alive.

The same analysis as the analysis of PFS RECIST 1.1 will be repeated for PFS from start of new anti-cancer therapy.

3.4.3.2 ORR from Start of New Anti-Cancer Therapy

For patients who started a new anti-cancer therapy, ORR from start of new cancer therapy is defined as the proportion of patients with a best response of CR or PR, following the start of new anticancer therapy. Patients not meeting this criterion will be considered non-responders. The same analysis as the analysis of ORR will be repeated for ORR from start of new anti-cancer therapy.

3.4.3.3 Progression-Free Survival 2

PFS2 is defined as the time (in months) from initiation of study treatment to the first occurrence of disease progression on next-line treatment or death from any cause, whichever occurs first. Patients who are alive and who have not experienced disease progression on next-line treatment at the time of clinical cut-off date will be censored at the last date known to be alive.

The same analysis as the analysis of PFS RECIST 1.1 will be repeated for PFS2.

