Exploratory objectives will include evaluation of the safety and efficacy of atezolizumab in patient subgroups differentiated by: presence or absence of CNS metastases at baseline; ECOG performance status; histological subtype; history of or current autoimmune disease; and prior anticancer treatment. Other exploratory and PRO outcomes will include objective response rate and progression-free survival 2 (PFS2) following start of new anticancer therapy, HR QoL as measured on the EORTC LQ-LC13, health utility score as measured on the EQ-5D-5L instrument, and expression of PD-L1 protein and cancer-related genes in tumor samples obtained before treatment. Finally, exploratory biomarkers may be assessed in tissue to assist in the potential development of new diagnostic assays and to assess biomarkers in terms of prognosis, response/resistance and safety.

Following discontinuation of study treatment, safety assessments will be conducted for 30 days after the last study drug administration or until initiation of other anti-cancer therapy (whichever occurs first). Thereafter, follow-up information on disease progression (unless this has already occurred), anti-cancer therapy and survival will be collected via telephone contact, patient medical records, and/or clinic visits approximately every 3 months until death, loss to follow-up, end of study (30 months after last patient in), patient withdrawal or study termination by the Sponsor, whichever occurs first. In addition, irAEs, SAEs and AESIs will be collected as described in Section [5.4.2](#).

In those patients for whom tumor assessments are performed as part of local clinical practice and are available for report after PD or atezolizumab treatment discontinuation, overall response rate (ORR) and progression-free survival (PFS) will be assessed from the first date of the new anticancer therapy to the end of the study. These data will be used in an exploratory fashion to assess whether prior atezolizumab treatment positively influences response to subsequent anticancer therapies.

An Independent Data Monitoring Committee (iDMC) will be established to review all AEs, irAEs, SAEs, AESIs and other cumulative safety data.

A Schedule of Assessments for this study is provided in [Appendix 1](#).

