4.5.6 Ongoing Tumor Assessments

Patients who discontinue study treatment early for reasons other than disease progression (e.g., toxicity) should continue to undergo scheduled tumor assessments (See [Appendix 1](#)) until the patient dies, experiences confirmed disease progression, withdraws consent, until study termination, or until the study closes, whichever occurs first.

Patients who start a new anti-cancer therapy in the absence of disease progression should continue to be followed for progression according to the protocol schedule of response assessments, unless consent is withdrawn or the patient experiences disease progression or death or until study termination or withdrawal from study, whichever occurs first.

In those patients for whom tumor assessments are performed as part of local clinical practice and are available for report after PD or atezolizumab treatment discontinuation, overall response rate (ORR) and progression-free survival (PFS) will be assessed from the first date of the new anticancer therapy to the end of the study. These data will be used in an exploratory fashion to assess whether prior atezolizumab treatment positively influences response to subsequent anticancer therapies.

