6.6.3 Exploratory Efficacy Analysis

The following efficacy endpoints will be evaluated to further assess the efficacy of atezolizumab after disease progression (no confirmation of response will be required for these analyses)

In those patients who received further anti-cancer therapy:

- Progression-free survival from start of new anti-cancer therapy, defined as the time from initiation of new anti-cancer therapy to objective tumor progression on next-line treatment or death from any cause
- Objective response rate from start of new anti-cancer therapy, defined as the percentage of patients who attain complete response (CR) or partial response (PR)

In the ITT population:

- Progression-free survival 2 (PFS2), defined as the time from initiation of study treatment to objective tumor progression on next-line treatment or death from any cause

The prior analyses might be repeated in the following subgroups, if enough patients are available:

- Presence of CNS metastases at baseline (yes vs. no)
- ECOG performance status (0 or 1 vs. 2)
- Histologic subtype (squamous vs. non-squamous)
- History of or current autoimmune disease (yes vs. no)
- Prior anticancer treatment

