3.4.1.4 Objective Response Rate

ORR, according to RECIST v1.1, is defined as the proportion of patients with a confirmed BOR, either CR or PR, as determined by the investigator using RECIST v1.1. Patients not meeting this criterion, including those without any post-baseline assessment, will be considered non-responders.

An estimate of ORR and its 95% CI will be calculated using the Clopper-Pearson method.

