- p. Patients will undergo tumor assessments at baseline, every 6 weeks \pm 5 days for the first 48 weeks following treatment initiation, and every 9 weeks thereafter until radiographic disease progression per RECIST v1.1 or (for patients who continue atezolizumab after radiographic disease progression) loss of clinical benefit as determined by the investigator (see Section 3.1.1 for details). Thus, tumor assessments are to continue according to schedule in patients who discontinue treatment for reasons other than disease progression or loss of clinical benefit, even if they start new anti-cancer therapy.
- q. For sites where EGFR/ALK testing is not routinely performed at local laboratories, a minimum of 7 consecutively cut slides from a most recent FFPE tumor tissue block must be submitted for EGFR/ALK testing for all patients with non-squamous NSCLC. Testing is not required for patients who have squamous NSCLC. EGFR mutation and ALK testing should be considered for patients with squamous NSCLC who are never-smokers, have mixed histology or small biopsy specimen.
- r. If available, pre-treatment FFPE tumor tissue (most recent sample) for PD-L1 testing and exploratory biomarkers. Most recent archival sample or a sample obtained during screening should be submitted if available (1 FFPE tissue block or 5–10 slides).
- s. From patients who received anti-PD-1 therapy, sites are highly encouraged to provide archival FFPE tissue (prior anti-PD1 therapy) and an FFPE tissue biopsy obtained during screening (archival and screening tissue sample).
- t. Ten milliliters (10 mL) whole blood for plasma. Not applicable for a site that has not been granted approval for RBR sampling. Performed only for patients at participating sites who have provided written informed consent to participate.
- u. Only to be shipped if the patient is eligible for enrollment.
- v. See Appendix 4.
- w. Concomitant medications include any prescription medications or over-the-counter medications. At screening, any medications the patient has used within the 7 days prior to the screening visit should be documented. At subsequent visits, changes to current medications or medications used since the last documentation of medications will be recorded.

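### Next-line ORR in SAP 3.4.3.2 counts starters with no tumor assessment as non-responders, although no scans are mandated once PD has occurred; the rate is a lower bound, and the documents disagree on its population

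*SAP*

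**What the plan says.** **The rule.** The denominator in SAP 3.4.3.2 is everyone who began another treatment for the cancer, with the rate "defined as the proportion of patients with a best response of CR or PR, following the start of new anticancer therapy". A separate sentence settles how all remaining starters are scored: "Patients not meeting this criterion will be considered non-responders". The section then carries over the analysis of the main ORR, which gives a 95% Clopper-Pearson interval. The main rule, in SAP 3.4.1.4, is explicit about patients who were never imaged: "Patients not meeting this criterion, including those without any post-baseline assessment, will be considered non-responders".

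**When scans stop.** Note p of the Schedule of Assessments (SAP Appendix 2; Protocol Appendix 1) runs imaging every 6 weeks for 48 weeks and "every 9 weeks thereafter until radiographic disease progression per RECIST v1.1", or until loss of clinical benefit in patients treated beyond progression. Later follow-up, in note y, is by telephone, records or visits about every 3 months and requires no scan. There is one exception, in Protocol 4.5.6: "Patients who start a new anti-cancer therapy in the absence of disease progression should continue to be followed for progression", on the protocol schedule.

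**Who is counted.** Two descriptions coexist.
- Protocol 3.1 introduces next-line ORR and PFS with "In those patients for whom tumor assessments are performed as part of local clinical practice and are available for report after PD" or after atezolizumab is stopped. Protocol 4.5.6, the protocol synopsis and the synopsis appended to the SAP carry the same restriction.
- Protocol 6.6.3 sets the population as "In those patients who received further anti-cancer therapy", with no scan condition and no rule for patients without a scan. SAP 3.4.3.2 follows this denominator and adds the non-responder rule.

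SAP section 3 states that the SAP takes precedence over the protocol, so the all-starters version is the one that would be run.

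**The concern.** For a patient who starts a new therapy after PD, a response can enter the database only if local practice produced a scan and the site reported it. The denominator has no matching condition. The resulting percentage therefore mixes two things: how often the next therapy worked, and how often someone looked and reported.

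The stated use of these data is exploratory: to judge whether earlier atezolizumab favours response to later treatment. A low figure could be read as poor response after atezolizumab when part of it is missing imaging. SAP 3.4.3.2 does not ask for the number of starters who were assessed, so a reader could not tell the two apart. The SAP does ask for completion rates for the questionnaires (SAP 3.4.2), but for nothing comparable here.

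The conflict over the population adds a practical problem: two programmers working from different sections would produce different denominators.

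**Working it through.** The documents give no expected next-line ORR, no number of starters and no share with a scan. There is thus no figure of the plan's to reproduce, and what follows is algebra with assumed ranges.

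**Definitions**
- s = share of starters with at least one tumor assessment after the new therapy began (not given)
- q = ORR among those assessed (not given)
- r = ORR in the unassessed divided by ORR in the assessed (not given)

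Recorded responses are taken as correct.

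**Formulas**
- SAP estimate: responders come only from the assessed and the denominator is everyone, so it equals s × q.
- True rate in all starters: q × [s + (1 − s) × r].
- Relative error of the SAP estimate: s / [s + (1 − s) × r] − 1.
- Relative error of an assessed-only estimate, which equals q: 1 / [s + (1 − s) × r] − 1.

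Since (1 − s) × r is never negative, the SAP error is never positive. It is zero when everyone is assessed or when no unassessed patient responds.

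**SAP estimate, relative error**

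| Assessed share s | r = 0 | r = 0.5 | r = 1 | r = 1.5 |
|---|---|---|---|---|
| 90% | 0% | −5% | −10% | −14% |
| 80% | 0% | −11% | −20% | −27% |
| 70% | 0% | −18% | −30% | −39% |
| 50% | 0% | −33% | −50% | −60% |

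Example: s = 0.5, r = 0.5 gives 0.5 / (0.5 + 0.25) − 1 = −33%.

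**Assessed-only estimate, for comparison.** At s = 0.5, r = 0.5 the error is 1 / 0.75 − 1 = +33%. At s = 0.8, r = 0.5 it is 1 / 0.9 − 1 = +11%. At r = 1 it is zero. If the unassessed do worse, this estimate is too high.

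**What the two would look like in a table.** Assume 200 starters and an ORR of 15% among the assessed (neither is in the documents). Intervals are 95% Clopper-Pearson.

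| Assessed | All starters (SAP) | Assessed only |
|---|---|---|
| 80% | 24/200 = 12.0% (7.8–17.3) | 24/160 = 15.0% (9.9–21.5) |
| 70% | 21/200 = 10.5% (6.6–15.6) | 21/140 = 15.0% (9.5–22.0) |
| 50% | 15/200 = 7.5% (4.3–12.1) | 15/100 = 15.0% (8.6–23.5) |

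The interval gives no warning. It reflects sampling error on 200 patients, not the missing assessments. With half assessed and r = 1, the true 15% lies above the upper limit of 12.1%.

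**The case against.** The case for leaving the SAP alone has real substance.

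- **The denominator has protocol support.** A reader of Protocol 3.1 might infer that the SAP departs from a single protocol definition. It does not: the protocol's own statistical section, 6.6.3, takes everyone who received further therapy. What exists is a conflict between sections, and the SAP sides with one of them. This stands.
- **Counting the unassessed as failures is the convention of the main ORR.** It errs in a known direction. In previously treated advanced disease, a patient who dies or deteriorates before the first scan on the next line is plausibly a true non-responder. This stands too, and it is why the loss may be small.
- **Restricting to the assessed selects on something that happens after the therapy starts.** It can drop early deaths and overstate response. This stands, so the assessed-only set should not simply replace the present analysis.
- **The endpoint is exploratory, in a single arm, with no stated benchmark.** Neither denominator can by itself show that atezolizumab helps later treatment. This limits how much the point matters. It does not remove the need to say how many patients were assessed.

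Two stronger readings are tempting and fail. One is that next-line responses are visible only where local scans exist. Protocol 4.5.6 keeps patients who start new therapy before PD on scheduled scans until PD, so this applies only to those who start after PD. The other is that the rate falls in proportion to the missing scans. That holds only at r = 1, which the documents do not support or address.

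**Conclusion.** The point holds in limited form. As written, SAP 3.4.3.2 gives a rate that cannot exceed the true next-line ORR and is too low whenever an unassessed starter responds. The direction is certain, provided recorded responses are correct. The size is not: it depends on the assessed share and on response among the unassessed, and the documents give neither. Over the ranges tried, the relative understatement runs from 0% to 60%.

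Separately, and without any assumption, the documents describe two different populations for the same endpoint. That needs reconciling whichever is chosen.

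This is a cheap improvement to an exploratory analysis. The primary safety endpoints and the 2-year OS rate are not touched.

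**What to change.** In SAP 3.4.3.2:

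1. State the population once, and reconcile it with the appended SAP synopsis and with Protocol 3.1, 4.5.6 and 6.6.3.
2. Report the number and percentage of new-therapy starters who had at least one tumor assessment after that therapy began.
3. Present ORR with its Clopper-Pearson interval on both denominators. Label the all-starters figure as a lower bound. Label the assessed-only figure as possibly too high, because patients who get scanned may be fitter.

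The cost is a change of SAP wording, one extra table row and a second exploratory estimate to explain. No new data are needed.
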